3 OBJECTIVES AND ENDPOINTS

Objectives and endpoints

Objectives	Endpoints
Primary objective	
Demonstrate the anti-tumor activity of BNT111 + cemiplimab (Arm 1) in terms of objective response rate (ORR) according to Response Evaluation Criteria in Solid Tumors (RECIST) 1.1.	ORR defined as the proportion of patients in whom a complete response (CR) or partial response (PR) is observed as best overall response by blinded independent central review (BICR).
Secondary objectives	
Assess the anti-tumor activity of each single agent (i.e., monotherapy of BNT111 and cemiplimab) in terms of ORR according to RECIST 1.1 (key secondary endpoint).	ORR defined as the proportion of patients in whom a CR or PR is observed as best overall response by BICR.
Assess additional measures of anti- tumor activity of BNT111 + cemiplimab (Arm 1), and each single agent (i.e., monotherapy of BNT111 and	 Duration of response (DOR) defined as the time from first objective response (CR or PR) to first occurrence of objective tumor progression (progressive disease, PD) by BICR or death from any cause (whichever occurs first).
cemiplimab) according to RECIST 1.1.	 Disease control rate (DCR) defined as the proportion of patients in whom a CR, PR or stable disease (SD; assessed at least 6 weeks [wks] +/- 1 wk after first dose) is observed as best overall response by BICR.
	 Time to response (TTR) defined as the time from randomization to the first objective tumor response (CR or PR) by BICR.
	 Progression-free survival (PFS) defined as the time from randomization to first objective tumor progression (PD) by BICR or death from any cause (whichever occurs first).
	 ORR, DOR, DCR, TTR, PFS, as assessed by the investigator.
Assess overall survival (OS) of BNT111 + cemiplimab (Arm 1).	 OS defined as the time from randomization to death from any cause.
Assess the safety and tolerability profile of BNT111 + cemiplimab (Arm 1), and each single agent (i.e.,	 Occurrence of treatment-emergent adverse events (TEAEs) within a patient including Grade ≥ 3, serious and/or fatal TEAEs by relationship.
monotherapy of BNT111 and	 Occurrence of immune-related adverse events (irAE).
cemipilmab).	 Occurrence of dose reduction and discontinuation of trial treatment within a patient due to a TEAE.
	 Changes in laboratory parameters compared to baseline*.
	 Occurrence of abnormal laboratory parameters within a patient.
	Changes in vital signs parameters compared to baseline*.

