8.4 Adverse events of special interest

An AESI, serious or non-serious, is one of scientific and medical concern specific to the sponsor's product or program, for which ongoing monitoring and rapid communication by the investigator to the sponsor are appropriate. Such an event might warrant further investigation in order to characterize and understand it. Depending on the nature of the event, rapid communication by the trial sponsor to other parties (e.g., regulators) might also be warranted.

The following AEs should be reported if related to cemiplimab:

- Grade ≥ 2 infusion-related reactions are considered AESIs and must be reported within 24 h of identification by the investigator.
- Grade ≥ 3 irAEs are considered AESIs and should be reported within 24 h of identification by the investigator.

Note: An irAE can occur shortly after the first dose or several months after the last dose of treatment. All AEs of unknown etiology associated with drug exposure should be evaluated to determine possible immune etiology. If an irAE is suspected, efforts should be made to rule out neoplastic, infectious, metabolic, toxin or other etiologic causes prior to labeling an AE as an irAE.

AESI including non-serious AESI should be reported via the SAE Report Form according to the timelines and contact details given in Section 10.3.1.10 of this protocol. For non-serious AESI, the seriousness criterion should not be reported/selected as these non-serious AESIs are to be reported according to the timelines of SAEs, but mostly do not have the seriousness of an SAE.

Page 86 of 133 Version: 7.0 Date: 09 FEB 2023

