9.4.5 Safety analyses

Safety data that will be summarized includes AEs, safety laboratory parameters, vital signs and ECGs. All safety analyses will be based on the safety set and will be summarized descriptively by treatment group unless otherwise stated.

Adverse events

AEs will be coded using the most recent version of Medical Dictionary for Regulatory Activities (MedDRA®) coding system to get a System Organ Class (SOC) and Preferred Term (PT) for each AE and graded for severity using NCI-CTCAE v5.0.

The number and percentage of patients reporting at least one AE will be summarized by PT nested within SOC for each of the following AE types:

- any AE
- related AE
- Grade ≥ 3 AE
- related Grade ≥ 3 AE
- any SAE

Page 95 of 133 Version: 7.0 Date: 09 FEB 2023

- related SAE
- SAE leading to death
- AEs leading to dose reduction
- AE leading to permanent discontinuation of treatment
- any irAE (listed in Appendix 12.1)

Moreover, the number and percentage of patients with any AE will be summarized by worst NCI-CTCAE grade by PT nested within SOC.

Laboratory parameters

Safety laboratory assessments to be summarized include hematology, blood chemistry, and urinalysis. The safety laboratory parameters to be assessed are listed in Section 10.2 and the scheduled time points for assessment are outlined in the SoAs (Section 1.3).

Safety laboratory parameters at each time point and change from baseline to each postbaseline time point will be summarized using descriptive summary statistics for each parameter by treatment group.

Safety laboratory results will be classified according to the most recent version of NCI-CTCAE. Shift tables from baseline to worst grade on treatment will be provided for each laboratory parameter by treatment group.

Additionally, the occurrence of clinically significant abnormal laboratory results within a patient will be analyzed using descriptive summary statistics for each parameter and visit by treatment group.

Laboratory results will be listed along with the normal ranges and NCI-CTCAE grade. Laboratory values that are below or above the normal ranges will be flagged.

Vital signs

Vital sign parameters and the scheduled time points for assessment are presented Section 8.2.3 and Section 1.3.

Vital sign parameters at each time point and change from baseline to each post-baseline time point will be summarized using descriptive summary statistics for each parameter by treatment group.

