3.1 Objectives and endpoints

Table 3.1 Trial Objectives

Objectives	Endpoints
Primary objective	Endpoint
Demonstrate the anti-tumor activity of BNT111 + cemiplimab (Arm 1) in terms of objective response rate (ORR) according to RECIST 1.1	 ORR defined as the proportion of patients in whom a complete response (CR) or partial response (PR) is observed as best overall response by blinded independent central review (BICR).
Secondary objectives	Endpoints
Assess the anti-tumor activity of each single-agent (i.e., BNT111 and cemiplimab, respectively) in terms of ORR according to RECIST 1.1 (key secondary endpoint)	 ORR defined as the proportion of patients in whom a CR or PR is observed as best overall response by BICR.
Assess additional measures of anti- tumor activity of BNT111 + Cemiplimab (Arm 1), and each single agent (i.e., BNT111 and cemiplimab) according to RECIST 1.1	 Duration of response (DOR) defined as the time from first objective response (CR or PR) to first occurrence of objective tumor progression (progressive diseases, PD) by BICR or death from any cause (whichever occurs first).
	 Disease control rate (DCR) defined as the proportion of patients in whom a CR, PR or stable disease (SD; assessed at least 6 weeks [wks] +/- 1 wk after first dose) is observed as best overall response by BICR.

Statistical Analysis Plan (SAP) BNT111-01

Page 13 of 78 Version: Final v7.0 Date: 05Mar2024

Objectives	Endpo	oints
Assess additional measures of anti- tumor activity of BNT111 + Cemiplimab (Arm 1), and each single agent (i.e., BNT111 and cemiplimab) according to RECIST 1.1	•	Time to response (TTR) defined as the time from randomization to the first objective tumor response (CR or PR) by BICR.
	•	Progression-free survival (PFS) defined as the time from randomization to first objective tumor progression (PD) or death from any cause, whichever occurs first by BICR.
	•	ORR, DOR, DCR, TTR, PFS, as assessed by the investigator.
Assess overall survival of BNT111 + cemiplimab (Arm 1)	*	Overall survival (OS) defined as the time from randomization to death from any cause.
Assess the safety and tolerability profile of BNT111 + Cemiplimab (Arm 1), as well as BNT111 and cemiplimab as single agents.	•	Occurrence of treatment-emergent adverse events (TEAE) within a patient including Grade ≥3, serious, fatal TEAE by relationship.
	•	Occurrence of immune-related adverse events (irAE).

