8.5.2 Adverse events

Adverse events (AEs) will be coded using Medical Dictionary for Regulatory Activities (MedDRA®) coding system version 23.1 or later to get a System Organ Class (SOC) and Preferred Term (PT) for each AE and graded for severity using NCI CTCAE v5.0. In case a patient has an AE with missing relationship status, the event will be assumed to be related and associated with the treatment received in the summaries (will be listed as collected in the listings). No imputation for missing NCI-CTC grades will be performed.

TEAEs for randomized treatment

A treatment-emergent AE (TEAE) is defined as any AE with an onset date on or after the first administration of trial treatment (if the AE was absent before the first administration of

Statistical Analysis Plan (SAP) BNT111-01

Page 46 of 78 Version: Final v7.0 Date: 05Mar2024

trial treatment) or worsened after the first administration of trial treatment (if the AE was present before the first administration of trial treatment). AEs with an onset date more than 90 days after the last administration of trial treatment will be considered as treatment emergent only if assessed as related to trial treatment by the investigator, prior to start of Add-on treatment, if applicable, whichever comes first.

An AE will be considered TE for the randomized treatment if it started within 90 days of last dose of randomized treatment or until start of add-on treatment whichever comes first.

Add-on TEAEs

Treatment-emergent for add-on treatment is defined as any AE with an onset date on or after the first administration of add-on treatment (if the AE was absent before the first administration of add-on treatment) or worsened after the first administration of the add-on treatment (if the AE was present before the first administration of add-on treatment). AEs with an onset date more than 90 days after the last administration of add-on treatment will be considered as TE only if assessed as related to add-on treatment by the investigator.

TEAEs for both randomized and add-on treatment

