Treatment emergent for both randomized & add-on treatment is defined as any AE with an onset date on or after the first administration of randomized treatment / add-on treatment (if the AE was absent before the first administration of randomized treatment / add-on treatment) or worsened after the first administration of randomized treatment / add-on treatment (if the AE was present before the first administration of randomized treatment / add-on treatment). AEs with an onset date more than 90 days after the last administration of randomized/add-on treatment will be considered as TE only if assessed as related to randomized/add-on treatment by the investigator. If an AE is treatment emergent for the randomized treatment and worsens in intensity during the Add-on treatment, the AE will appear only once in the summary.

TEAEs for randomized, add-on TEAEs and TEAEs for randomized and add-on treatment will be summarized by treatment group and overall for patients in the Safety analysis set and the Add-on Treatment set.

Adverse Events of Special Interest (AESI)

- Grade ≥2 infusion-related reactions related to cemiplimab are considered AESIs.
- Grade ≥3 irAEs (immune-related AEs) related to cemiplimab are considered AESIs.

Overall summary of adverse events (AE)

The number and percentage of patients reporting at least one AE will be summarized for each of the following AE types (summary applies to both BNT111 and cemiplimab unless otherwise specified):

- Any AE
- TEAE
- Related TEAE (BNT111, cemiplimab and both)

Page 47 of 78 Version: Final v7.0 Date: 05Mar2024

- Grade ≥3 TEAE
- Related grade ≥3 TEAE (BNT111, cemiplimab and both)
- Any TESAE
- Related TESAE (BNT111, cemiplimab and both)
- TESAE leading to death
- Related TESAE leading to death (BNT111, cemiplimab and both)
- Any AESI
- Grade≥ 2 infusion-related reactions (IRRs) related to cemiplimab
- Grade≥ 3 irAEs (immune-related AEs) related to cemiplimab
- TEAEs leading to dose reduction (BNT111)
- TEAEs leading to dose interruption (BNT111, cemiplimab and both)
- TEAEs leading to permanent discontinuation of treatment
- Related TEAEs leading to dose reduction (BNT111)
- Related TEAEs leading to dose interruption (BNT111, cemiplimab and both)
- Related TEAEs leading to permanent discontinuation of treatment

Analyses of adverse events

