The number and percentage of patients reporting TEAEs will be summarized by PT nested within SOC. If a SOC / PT is reported more than once for a patient, the patient will only be counted once for this SOC / PT. Strongest relationship or worst grade will be counted if a TEAE is reported more than once by the same patient for a SOC / PT.

All AE summary tables will be presented for BNT111 and cemiplimab separately and sorted alphabetically by SOC and PT within SOC.

Analyses of other adverse events (excluding serious AEs)

The number and percentage of patients reporting other TEAEs (excluding TESAEs) will be summarized by PT nested within SOC. If a SOC / PT is reported more than once for a patient, the patient will only be counted once for this SOC / PT.

All AE summary tables will be presented for BNT111 and cemiplimab separately and sorted alphabetically by SOC and PT within SOC.

Treatment-related AEs

The number and percentage of patients reporting treatment-related TEAEs will be summarized by PT nested within SOC for BNT111 and cemiplimab separately and related to both the treatments.

Statistical Analysis Plan (SAP) BNT111-01

Page 48 of 78 Version: Final v7.0 Date: 05Mar2024

In addition, treatment-related for both randomized and add-on treatment TEAEs will be summarized by PT nested within SOC for BNT111 and cemiplimab separately.

AESIs (irAE and Infusion-related AEs)

The number and percentage of patients with AESIs, irAEs grade ≥3 related to cemiplimab and infusion-related reactions grade ≥2 related to cemiplimab will be summarized by PT nested within SOC.

TEAE by NCI-CTCAE grade

The number and percentage of patients with TEAEs will be summarized by worst NCI-CTCAE grade by PT nested within SOC. Worst grade will be counted if a TEAE is reported more than once by the same patient for a SOC / PT.

TEAE by NCI-CTCAE grade by relationship status

The number and percentage of patients with related and not related TEAEs will be summarized by worst NCI-CTCAE grade by PT nested within SOC for BNT111 and cemiplimab separately. Worst grade will be counted if a TEAE is reported more than once by the same patient for a SOC / PT.

Serious Adverse Events

The number and percentage of patients with TESAEs will be summarized by PT nested within SOC.

Related Serious Adverse Events

The number and percentage of patients with related TESAEs (for BNT111 and cemiplimab separately and related to both the treatments) will be summarized by PT nested within SOC.

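### The SAP safety tables summarise immune-related adverse events only if Grade 3 or higher and related to cemiplimab, so the any-irAE summary planned in the protocol is missing and its omission is undeclared

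*SAP*

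**What the plan says.** The protocol (section 3) sets the secondary safety objective: "Assess the safety and tolerability profile of BNT111 + cemiplimab (Arm 1), and each single agent". One of its endpoints, repeated in SAP Table 3.1, is "Occurrence of immune-related adverse events (irAE"), with no restriction by grade, drug or causality.

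Protocol 9.4.5 plans counts with percentages: "patients reporting at least one AE will be summarized by PT nested within SOC for each of the following AE types"; the last type listed is "any irAE (listed in Appendix 12.1"). Appendix 12.1 (Table 16) defines irAEs by a list of preferred terms, without a grade or attribution condition. Protocol 8.3.8 asks investigators to consider how irAEs relate to either drug, not to cemiplimab alone.

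SAP 8.5.2 contains two irAE summaries: one row in the overall adverse event table and one table by preferred term within system organ class. Both cover the same subset, "Grade ≥3 irAEs (immune-related AEs) related to cemiplimab"; for the second, the text is "irAEs grade ≥3 related to cemiplimab and infusion-related reactions grade ≥2 related to cemiplimab will be summarized". The listings paragraph of 8.5.2 includes all irAEs.

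**The concern.** The subset that the SAP summarises is the category of adverse events of special interest (AESI). Protocol 8.4 introduces that category for expedited reporting: "The following AEs should be reported if related to cemiplimab". It serves pharmacovigilance and is narrower than the endpoint. In the SAP tables it has taken the endpoint's place.

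Two things are at stake. First, a stated secondary endpoint is only partly summarised. All Grade 1 and 2 irAEs, and every irAE of any grade not attributed to cemiplimab, are left out of the irAE summaries. Second, the BNT111 monotherapy arm shows a zero that carries no information, and a reader of the report could take it for an observed absence of irAEs.

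The change is also silent. Protocol 9.4 requires departures from the final SAP to be justified in the trial report. An omission built into the SAP is not such a departure, so that safeguard would not bring it to light.

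**Working it through.** No figure in the plan needs reproducing; the check compares planned outputs.

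| Item | Protocol 9.4.5 and section 3 | SAP 8.5.2 |
|---|---|---|
| Grade | any | 3 or higher |
| Relationship | any | cemiplimab only |
| Arms covered in substance | all three | Arms 1 and 3, and add-on |
| Count and percentage of patients with any irAE | planned | absent from the safety tables |
| Any irAE by preferred term within system organ class | planned | absent |
| All irAEs | not applicable | listing only |

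**Is the omission declared?** SAP Appendix 1 has four entries: the Add-on Treatment set, duration of disease control, the Non-CR/Non-PD category, and removal of the time-to-deterioration analyses of the EORTC QLQ-C30. The last shows that dropped secondary analyses are meant to be declared there. None of the four concerns irAEs, and the SAP version history records no removal of an irAE summary.

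**Arm 2 before add-on.**
1. The row counts only irAEs related to cemiplimab.
2. Arm 2 patients receive no cemiplimab until add-on.
3. A missing relationship cannot fill the row, because "the event will be assumed to be related and associated with the treatment received in the summaries", which here is BNT111.
4. The count is therefore zero whatever occurs, provided that no event is attributed to a drug not given.

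**Can the total be rebuilt from the general tables?** SAP 8.5.2 tabulates all treatment-emergent events by preferred term, worst grade and relationship. A patient with two Appendix 12.1 terms appears in two rows. If two such rows count a and b patients in an arm of N, the number with at least one of the two terms lies between max(a, b) and min(N, a + b). The rows bound the total but do not give it. Table 16 has 225 preferred terms under 67 composite terms (counted from the extracted text), so such overlap is possible across many rows.

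**Can the total be read elsewhere?** SAP 7.3 defines occurrence of irAE (yes or no) as a subgroup factor for ORR, DCR and PFS. The analysis runs if each category has at least 10 Arm 1 patients; Arms 2 and 3 are then produced whatever their numbers. With 90 planned Arm 1 patients, and if all of them are in the analysis set:
- fewer than 10 with an irAE, below 10/90 = 11.1%: not run;
- 10 to 80 with an irAE, 11.1% to 80/90 = 88.9%: run;
- more than 80, above 88.9%: not run, since fewer than 10 remain without one.

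When it is run, the subgroup denominators show how many patients in each arm had an irAE. They give no breakdown by term.

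**The case against.** The strongest reply is that little is missing. Every irAE is listed, and each preferred term appears in the general tables by grade and drug. The any-irAE count by arm, BNT111 monotherapy included, can be read from the SAP 7.3 subgroup denominators over a wide range of rates.

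Much of this stands, and it rules out several stronger readings:

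- A reader might infer that irAE information is lost, or that the any-irAE count appears nowhere. The documents do not support that. What holds is that no safety table gives the total or its breakdown. The subgroup table is an exploratory efficacy output whose analysis set is blacked out, and its irAE window, treatment plus safety follow-up, may reach into add-on. It does not replace the planned safety summary.
- A reader might infer that the data monitoring committee is left unaware of these events. SAP 5.1 sends it the 8.5.2 presentations, which include the irAE listing and all the general tables. It lacks an aggregate, not the cases.
- A reader might take Arm 2's share, 45 of 180 patients (25%), as the size of the problem. That is the planned allocation, not a count of patients with unreported irAEs.
- A reader might see a present error in SAP 8.1, which anchors imputed irAE onset dates to the first cemiplimab dose. For the cemiplimab-related summaries now planned it does no harm. It matters only once all irAEs are summarised.

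It can also be said that an unrestricted count is non-specific. Appendix 12.1 includes diarrhea, rash, raised ALT, arthralgia and myalgia, and Protocol 8.4 wants other causes excluded before an event is labelled an irAE. That is a reason for a footnote. It does not remove a summary that the protocol defines by this very list.

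**Conclusion.** The point holds as a discrepancy between protocol and SAP that should be corrected. The protocol plans an any-irAE summary for an unrestricted secondary endpoint. The SAP replaces it with the AESI subset, does not declare the change, and so produces an uninformative zero for BNT111 monotherapy before add-on.

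The consequence is limited to safety reporting. The primary efficacy analysis and its type I error are untouched, and the underlying data are kept. The number of patients affected cannot be derived from the documents, which give no expected irAE rate for these arms by grade and attribution. The conclusion rests on SAP 8.5.2 being followed as written; none of the text compared here is blacked out.

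A reader might think one line in Appendix 1 would be enough. It would make the change visible, but the secondary endpoint would still be only partly summarised.

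**What to change.** Add to SAP 8.5.2:

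1. An any-irAE row in the overall adverse event summary: Appendix 12.1 terms, all grades, regardless of relationship.
2. An any-irAE table by preferred term within system organ class, by arm, for the Safety set and the Add-on Treatment set.
3. A footnote that the Appendix 12.1 list is non-specific (for example diarrhea, rash, ALT increased, arthralgia, myalgia) and that some terms overlap with the flu-like symptoms expected with BNT111 (Protocol 6.8.4.1).

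Keep the AESI row and table as they are.

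With this addition, the SAP 8.1 irAE date rule needs a provision for patients who have not received cemiplimab, for example anchoring to the first dose of any trial treatment in the randomized period. Otherwise a partial Arm 2 onset date could be placed before the first BNT111 dose, or a monotherapy event moved into the add-on period.

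The cost is one row, one table, a footnote and a change of wording. The events are already collected and coded, and SAP 7.3 already defines an irAE yes/no variable.
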